reporting and to improve the transparency of the data collection and analysis phases of these two studies, we decided to write this statistical analysis plan before any statistical analyses were conducted. The study results will be reported according to The Transparent Reporting of a multivariable prediction model for Individual Prognosis Or Diagnosis (TRIPOD) -statement.³²

Objectives and hypotheses

The objectives of the first study:

- To determine the rate of secondary surgery due to fracture nonunion of AO/OTA type A and C distal femur fractures treated primarily with lateral locking plate
- To evaluate how accurately the previously identified patient- and injury-related risk factors predict a distal femur fracture nonunion

The objective of the second study:

- To evaluate how accurately the previously identified treatment-related risk factors predict a distal femur fracture nonunion
- To evaluate a secondary prediction model combining the treatment-related risk factors and the three most important patient- and injury-related predictive factors from the first study

STUDY METHODS

This study is a retrospective cohort study conducted in level 1 trauma centre at the Helsinki University Hospital with a catchment population of around one million for these fractures. After receiving permission from our institutional review board, we identified all patients with a distal femur fracture treated at our institution between 2009 and 2018 using the electronic patient record system. Both of our future articles regarding the prediction of distal femur fracture nonunion will use the same patient data.

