4. Empty holes adjacent the fracture site (i.e., on the intact part of the femur)

5. Plate span ratio: defined as a ratio of the plate length to the fracture length
6. Proximal plate length: Defined as number of plate holes proximal to the fracture lines in X-ray
7. Proximal fixation mode: locking screws, locking + cortical screws (hybrid), cortical screws, cables with or without screws
8. Proximal cortices: Defined as the number of proximal cortices fixed with screws or cables above the fracture segment. One cable is defined to correspond to a bicortical screw (i.e., purchase of 2 cortices). The sufficient proximal fixation is defined as a purchase of 8 or more cortices (e.g., minimum of 4 bicortical screws) and a purchase of less than 8 cortices is defined as not sufficient.
9. The number of locking screws in the plate crossing the fracture segment

Table 2. Data set used in the study.
Patient-related factors (Study I)

 - Age at the date of injury - Sex - Body mass index - Diabetes - Smoking
Injury-related factors (Study I)

 - AO/OTA^a classification - Periprosthetic fracture above a knee prosthesis - Open/closed fracture - Trauma energy - Fracture zone length - Segmental comminution (AO/OTA A3, C2, C3) - Medial comminution of the fracture
Treatment-related^b factors (Study II)

 - Plate length in millimetres - Plate working length - Empty holes adjacent the fracture site - Plate span ratio - Proximal plate length - Proximal fixation mode - Proximal cortices - Locking screws in the fracture segment

^a AO/OTA = The AO Foundation/Orthopaedic Trauma Association

^b See text for definition

STATISTICAL PRINCIPLES

Our statistical analysis is based on predictive approach, and we will follow guidelines from Harrell and Heinze et al.^{36,37} We will use logistic regression since our outcome is binary. Our analysis will be three-fold as outlined above. In the first analysis, we will model risk of nonunion using patient- and injury-related variables. In the second analysis, we will use treatment-related variables. The third analysis will be a combined model which include 3–4 most important variables from the first analysis combined with the 3–4 most important from the second model.

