Background knowledge based on previous literature was used to form initial set of variables which may be predictive for nonunion. Variable missingness is assessed. We assume Missing Completely at Random (MCAR) for any missing data and multiple imputation is used. Imputation is based on both predictors and outcome variable. Redundancy analysis is then performed to assess any collinearity between predictors and data reduction is performed if reasonable. Binary variables with very high skewness are critically assessed and excluded from final variable set if seen feasible. Model fitting will be done with imputed datasets. For fitted models, overall R² is estimated and used to interpret the applicability of baseline predictors. Variable importance is also assessed using Wald chi-squared test minus degrees of freedom. Calibration plots will be printed for all three models. Multiplicity is not considered since we are not focused in single regression coefficients nor we have specific multiple testing. When appropriate, 95% confidence intervals will be calculated, and associated p-values calculated. Analysis is done with RStudio using rms package.

REFERENCES

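### The aim is predictive accuracy, but the SAP commits to no internal validation, optimism correction or discrimination measure, so the R² it relies on is optimistic on average

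*SAP*

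**What the plan says.** Under Objectives and hypotheses, the second aim of Study I is "To evaluate how accurately the previously identified patient- and injury-related risk factors predict a distal femur fracture nonunion". Study II has the matching aim for treatment-related factors, plus a secondary model that combines the two groups. Under Study Methods, both papers draw on one cohort.

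Statistical Principles plans logistic regression and two performance outputs. The first is R²: "For fitted models, overall R² is estimated and used to interpret the applicability of baseline predictors". The second is graphical: "Calibration plots will be printed for all three models". Variables are ranked on the fitted models: "Variable importance is also assessed using Wald chi-squared test minus degrees of freedom". The third analysis is a "combined model which include 3–4 most important variables from the first analysis combined with the 3–4 most important from the second model".

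Two steps could reduce the number of parameters, and both are conditional: "data reduction is performed if reasonable", and "Binary variables with very high skewness are critically assessed and excluded from final variable set if seen feasible". Missing values are multiply imputed: "Imputation is based on both predictors and outcome variable".

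The SAP cites TRIPOD for reporting, two methodological guides and the rms package. It takes no validation step from any of them. Bootstrap, cross-validation, split sample, optimism, shrinkage, C-statistic, ROC curve and Brier score are not mentioned.

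**The concern.** A model fitted by maximum likelihood follows the noise in its own data as well as the signal, so R² in those data overstates, on average, what the model would explain in new patients. The SAP gives this figure the job of showing whether the predictors are applicable.

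Model 3 carries a second layer. Its variables are those that ranked highest in models 1 and 2, and they are refitted on the patients who produced the ranking.

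The calibration plots do not show the problem unless they are bias-corrected, and the SAP does not say that they are. In a single completed dataset a maximum-likelihood logistic model has calibration intercept 0 and slope 1 by construction. After pooling over imputations this holds approximately.

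At stake are the accuracy aims of both studies. The rate of secondary surgery, the first aim of Study I, is not affected. The background text says the model could be used in practice to advise patients, so overstated accuracy might carry into that use.

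**Working it through.** The SAP gives no sample size, event count or expected R², so there is no figure of its own to reproduce. The check asks how large the optimism could be.

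**Inputs from the SAP.** Nonunion is 10–22% in most cited series and 6% in a cited meta-analysis. Table 2 lists 12 Study I variables, taken as 12 parameters, and 8 Study II variables, taken as 10 because fixation mode has four levels.

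**Assumptions.** N is 200 to 400. R² is Nagelkerke's. Predictors are independent, about half of them have no effect, and the linear predictor has SD 0.8 (weaker signal) or 1.3 (stronger). Model 3 takes the top three variables from each of models 1 and 2 by Wald chi-square minus degrees of freedom. Reduced parameter sets of 8+6 and 4+4 stand for data reduction.

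**Step 1: no true effect.** The expected likelihood-ratio chi-square is about df, so expected R² ≈ (1 − exp(−df/N)) / (1 − exp(2·l0)), with l0 = p ln p + (1 − p) ln(1 − p). For df = 12, N = 300, p = 0.10: l0 = −0.325, and R² ≈ 0.0392 / 0.478 = 0.08. The same formula gives 0.16 for N = 200, 6%, and 0.045 for N = 400, 22%. The true value is 0 each time.

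**Step 2: simulation with a true signal.** Mean R² is shown as fitted / df-adjusted / new patients. The df-adjusted value puts chi-square minus df into the formula. New-patient R² is taken after recalibration, which favours the plan. Each row has 200 to 250 replicates.

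| Row | N, rate (events) | Signal, parameters | Model 1 | Model 2 | Model 3 |
|---|---|---|---|---|---|
| A | 400, 22% (88) | stronger, 4+4 | 0.17/0.15/0.14 | 0.17/0.15/0.14 | 0.33/0.31/0.29 |
| B | 400, 22% (88) | stronger, 8+6 | 0.18/0.15/0.12 | 0.16/0.14/0.13 | 0.27/0.26/0.21 |
| C | 300, 22% (66) | stronger, 12+10 | 0.20/0.15/0.10 | 0.20/0.15/0.11 | 0.28/0.25/0.16 |
| D | 300, 10% (30) | weaker, 12+10 | 0.14/0.06/0.02 | 0.13/0.06/0.03 | 0.19/0.15/0.04 |
| E | 200, 6% (12) | weaker, 4+4 | 0.11/0.06/0.03 | 0.11/0.06/0.03 | 0.21/0.13/0.05 |
| F | 200, 6% (12) | weaker, 12+10 | 0.24/0.08/0.01 | – | 0.26/0.18/0.02 |

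Gap, fitted minus new patients:
- Row A: 0.17 − 0.14 = 0.03 for models 1 and 2, and 0.33 − 0.29 = 0.04 for model 3. A repeat run gave 0.02–0.03 and 0.04.
- Row D: 0.12 and 0.10 for models 1 and 2, and 0.15 for model 3. A repeat run gave 0.13 − 0.02 = 0.11 for model 1 and 0.18 − 0.04 = 0.14 for model 3.
- Row F: 0.23 for model 1 and 0.24 for model 3.

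Fitted R² fell below new-patient R² in no sample in row D, in 12%, 26% and 9% of samples (models 1, 2, 3) in row B, and in about 23–32% in row A.

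**Step 3: would a df-adjusted R² be enough?** For models 1 and 2 it removes much of the gap (model 1: 0.12 to 0.04 in D, 0.08 to 0.03 in E). For model 3 it removes about a quarter when many variables are screened (0.15 to 0.11 in D, 0.12 to 0.09 in C) and about half when few are (0.16 to 0.08 in E, 0.04 to 0.02 in A). Selection explains the difference. With no true effect and N = 300, model 3 shows R² of 0.11 at 10% nonunion, against 0.04 for six prespecified variables, and df adjustment still leaves 0.06.

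**Step 4: discrimination and calibration.** Model 1's C-statistic is 0.73 fitted against 0.60 in new patients in row D, and 0.73 against 0.69 in row B. Its new-patient calibration slope is 0.38 in D and 0.83 in B.

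**Step 5: does the remedy work?** Imputation, ranking, selection and refitting were repeated in each bootstrap resample, in 80 datasets with 60 resamples each. R² fitted → corrected (new patients) was:
- Row D: model 1 0.16 → 0.02 (0.02), model 3 0.19 → 0.04 (0.04).
- Row C: model 1 0.21 → 0.11 (0.10), model 3 0.28 → 0.17 (0.16).
- Row B: model 1 0.18 → 0.13 (0.12), model 3 0.29 → 0.22 (0.21).
- Row E: model 1 0.14 → 0.03 (0.02), model 3 0.23 → 0.04 (0.05).

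Fitted values differ slightly from the table because of imputation and new seeds. The corrected C-statistic of model 3 in row D stayed high: 0.77 → 0.67, against 0.61 in new patients. Model 2 and the corrected slope and intercept were not checked.

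**The case against.** The strongest defence is that the SAP is terse rather than wrong. It promises TRIPOD reporting, adopts two modelling guides and names a package, and analysts working in that tradition may well validate. It never says that R² is uncorrected. A reader might infer that the authors have ruled validation out, and the text does not support that: it is silent. But the SAP says it was written to prevent selective reporting, and general citations leave the choice open until results are seen.

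A second defence is that the simulated models are too large. Segmental comminution is derived from the AO/OTA class, and plate span ratio from plate length and fracture length, so the redundancy analysis would probably remove parameters. This stands: independent predictors may overstate how many remain, and the 12+10 rows are pessimistic. Reduction lowers the optimism but does not measure it, and with few events a gap remains even at 4+4 (row E).

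Third, a df-adjusted R² may be intended. If so, much of the problem for models 1 and 2 goes, and about half of it for model 3 when few variables are screened. A flat statement that adjustment does little for model 3 would be wrong. The SAP does not name the type, and adjustment for the fitted parameters does not account for the search behind model 3.

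Finally, no threshold or decision hangs on R², the largest gaps mostly concern a model the SAP calls secondary, and clinical use is mentioned only as a possibility. These points lower the severity. They do not remove the concern.

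**Conclusion.** The point holds. The SAP sets accuracy as the aim and judges it on a figure that, as written, comes from the fitting data, with no correction and no discrimination measure. The direction is clear on average, and model 3 is more exposed than models 1 and 2.

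The size is conditional on N, events, type of R² and data reduction, none of which is stated. Under the assumptions above, the mean gap runs from about 0.02–0.03 (models 1 and 2) and 0.04 (model 3) in row A to about 0.11 and 0.14 in row D, and it is larger with fewer events and no reduction.

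A reader might infer that the published accuracy is bound to be grossly inflated. The documents do not support that. With a large cohort, many events and few parameters the gap is modest, and the fitted figure falls below the new-patient figure in roughly a quarter to a third of samples. This should be fixed, but it does not invalidate the plan.

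**What to change.** In Statistical Principles, replace the R² sentence with:

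> For each of the three models, R² (type named), the C-statistic and the calibration slope and intercept will be reported with bootstrap optimism correction, and calibration curves will be bias-corrected. Imputation, any outcome-dependent data reduction and, for model 3, the ranking and selection of variables will be repeated in each resample. The applicability of the predictors will be judged on the corrected values.

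A bootstrap can repeat only a fixed rule. State one selection rule for model 3 (criterion and number of variables from each source), and reconcile Objectives and hypotheses (three Study I factors with the treatment-related factors) with Statistical Principles (three to four from each model).

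The cost is wording and computing time, with no new data. Combining imputation and selection with the bootstrap needs a short custom loop. Reported performance will look less favourable. With few events the corrected values remain imprecise and the C-statistic somewhat optimistic, which the report should say.

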Table 1. Inclusion and Exclusion criteria used in the study.

Inclusion

- Age > 16 years- AO/OTA type A or C distal femur fracture- Fracture located on the metaphyseal area of the distal femur (square method)- Operative treatment in the Helsinki University Hospital with a distal femur anatomic lateral locking plate- Operative treatment within 1 month after trauma- Operative treatment between years 2009 and 2018
Exclusion

- Stress fracture- Pathological fracture- An epicondylar or subchondral fracture- A ligament sprain in distal femur- Treatment with a double-plating method or with both plate and nail- Non-surgical treatment and patients who died before the treatment- Treatment with an unconventional plate (other than distal femur plate)- Patients whose follow-up criteria not fulfilled

Data collection

The details of the data used in this study are shown in Table 2.

The principles of the injury-related factors are as follows. Distal femur fractures were classified according to the AO/OTA classification system 2007.³³ High energy trauma was defined as a motor-vehicle accident or a fall from a height of >1m. Low-energy trauma was defined as a fall from a height of < 1m such as a fall from the same level or a fall from a chair or a bed. All fractures were classified as open or closed injuries. Open fracture was defined as a fracture with an open wound or break in the skin near the broken bone. The definition for a periprosthetic fracture in this study was a distal femur fracture above a knee prosthesis. Segmentally comminuted fractures were defined as A3, C2 and C3- fractures according to the AO/OTA-classification. The definition for medial fracture comminution was that more than one fracture line reached the medial cortex on the antero-posterior x-ray forming one or more loose bone fragments on the medial side. Fracture zone length was measured from the postoperative x-rays where the fracture was reduced. The known plate length in millimetres was used to correctly calibrate the x-ray.

The principles of the treatment-related factors are as follows.

1. The x-ray was calibrated using the plate length
2. Plate length in millimetres: Measured as the plate shaft holes first and then in millimetres given from the manufacturer
3. Plate working length: Defined as a distance from the nearest proximal screw to the nearest distal screw on each side of the fracture

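### Ranking predictors by Wald chi-square minus df gives almost no credit to a factor level with no events or only events, so a predictive sparse factor can be ranked too low for the combined model

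*SAP*

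**What the plan says.** STATISTICAL PRINCIPLES sets out three models. The method is given as "We will use logistic regression since our outcome is binary", with no penalised or Firth likelihood mentioned. Importance is described in one sentence: "Variable importance is also assessed using Wald chi-squared test minus degrees of freedom". The overall R² is the other summary, but it describes a whole model, not a variable.

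Importance then has a use: "The third analysis will be a combined model which include 3–4 most important variables from the first analysis", together with 3–4 from the second. The section Objectives and hypotheses words the first part as "the three most important patient- and injury-related predictive factors from the first study". No sentence says that Wald minus df is the entry rule, but no other variable-level criterion is offered.

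The rule on sparse predictors reads "Binary variables with very high skewness are critically assessed and excluded from final variable set if seen feasible". Among the treatment-related factors in Data collection is one with four categories: "Proximal fixation mode: locking screws, locking + cortical screws (hybrid), cortical screws, cables with or without screws".

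**The concern.** In maximum-likelihood logistic regression, a level with no events or only events has no finite coefficient. The iterations stop at a large coefficient with a far larger standard error, and their squared ratio is practically zero. The Wald statistic then reads as no evidence although the likelihood may change a good deal when the factor is removed (the Hauck–Donner effect). For a 1-df factor, Wald minus df becomes −1, the lowest score it can take.

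Two things make this relevant here. The rule for skewed variables is discretionary, looks at the predictor's own distribution rather than its cross-table with nonunion, and works by exclusion, so it does not rescue a sparse predictive factor. It also does not reach a four-level factor. At stake is the ranking reported in each article and the make-up of the combined model.

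**Working it through.** **Inputs.** Nonunion rates come from the SAP's background: 4% in a geriatric cohort (Risk factors for non-union), and 6% in a meta-analysis and 10–22% across studies (opening text). The SAP states no sample size, event count or level frequencies, so there is no figure of its own to reproduce. Every N and level size below is an assumption.

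**1. Why Wald collapses.** For a 2×2 table with cells a, b, c, d, the log odds ratio is β = log(ad/bc), its variance is 1/a + 1/b + 1/c + 1/d, and Wald = β²/variance. As a → 0, β² grows like (log a)² but the variance grows like 1/a, so Wald → 0. The LR statistic, the difference in −2 log L with and without the factor, stays finite:

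- 0/30 versus 25/170: 150.71 − 141.97 = 8.7; Wald 0.0.
- 5/5 versus 20/195: 150.71 − 128.97 = 21.7; Wald 0.0.

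**2. Sensitivity to one patient** (N = 200, 20 events, binary factor):

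| Events in the level | Wald − df | LR − df |
|---|---|---|
| 8/8 | −1.0 | 39.3 |
| 7/8 | 16.0 | 27.9 |
| 0/40 | −1.0 | 8.5 |
| 1/40 | 1.5 | 3.1 |

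In 1000 simulated nine-predictor models per table, the factor with the 8/8 or 0/40 level was never in the Wald top four and was last in 95% and 97% of runs. LR minus df put it in the top four in 100% and 99.9%. These results are conditional on such a table having occurred.

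**3. Four-level factor, 3 df** (N = 200):

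| Level sizes | Events | Wald − df | LR − df |
|---|---|---|---|
| 90/60/42/8 | 6/4/2/8 | −2.8 | 37.5 |
| 90/80/10/20 | 10/10/0/0 | −2.9 | 4.0 |
| 90/80/10/20 | 10/8/0/2 | −2.9 | −0.8 |
| 90/80/10/20 | 6/5/0/1 | −2.9 | −1.6 |
| 90/80/10/20 | 4/4/0/0 | −3.0 | −0.3 |

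The two statistics disagree in sign in the first two rows. In the last three, LR also scores the factor below zero.

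**4. How often a level is empty if fixation mode has no effect.** For m patients at rate p, P(no event) = (1 − p)^m. Over levels of size m_i, P(some level empty) = 1 − ∏[1 − (1 − p)^(m_i)]. With levels 90/80/10/20:

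| Rate | Level of 10 empty | Level of 20 empty | Some level empty |
|---|---|---|---|
| 4% | 66% | 44% | 82% |
| 6% | 54% | 29% | 68% |
| 10% | 35% | 12% | 43% |
| 22% | 8% | 0.7% | 9% |

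Keeping the same proportions and letting N run from 150 to 300, the range is about 2% to 90%.

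**5. If fixation mode does matter.** Assume risks of 12% in the two large levels and 2% in the two small ones, sizes 90/80/10/20. In about 60% of simulated samples LR minus df is above 2 while Wald minus df is below 0.

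**The case against.** The strongest reply is that the probabilities in step 4 do not measure harm. They apply one rate to every level, so fixation mode has no effect and a low rank is then correct. A reader might take 82% as the chance of losing a real predictor; it is not. This stands.

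It also stands that one empty level of about 10 carries little information: a binary factor with 0/10 and 20 events overall has LR minus df of only 1.2, and the four-level tables with just that level empty are negative under LR too. At a 10% common rate, both small levels are empty in about 0.35 × 0.12 ≈ 4% of samples.

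A reader might infer that the strongest sparse factor will be ranked last and dropped. The documents do not support that. It needs an all-events level, which is rare (5/5 at a 10% rate: 0.1⁵ = 0.00001, without an effect), or a large empty level of about 40. In a multi-level factor the contrasts among the other levels survive, so it need not come last. Nor does the SAP show that the cortical-only or cable groups are small; Surgical treatment says only that cables were used in fractures near an implant.

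Two further replies carry part of their weight. The SAP also allows data reduction where reasonable, which could be read to permit merging levels, though it is tied to the redundancy analysis and gives no rule. And the use of Wald minus df for entry to the combined model is inferred.

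What the objection does not remove is step 5: with a real effect and plausible sizes, the two statistics often disagree, and the one named is the one that fails.

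**Conclusion.** The point holds as a conditional weakness that is worth correcting. The only variable-level importance measure in the SAP gives about zero credit to a level with no events or only events, and the ranking can turn on a single patient (−1.0 for 8/8, 16.0 for 7/8). A predictive sparse factor can therefore be ranked too low and may miss the combined model.

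Its size cannot be fixed from the document. It rests on assumed N and level sizes, on the cited 4–22% rates, and on reading the importance sentence as the basis for entry. Under the assumed 12% versus 2% risks, the statistics conflict in about 60% of samples. Whether that would change the top three or four depends on the other predictors' scores, which are unknown.

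**What to change.** In STATISTICAL PRINCIPLES, replace Wald with likelihood-ratio chi-square minus df, pooled over imputations by a named method, and state that this ranking decides entry to the combined model. Before fitting, merge sparse levels of multi-level factors such as proximal fixation mode, using level counts and subject-matter similarity and blind to nonunion.

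If Firth likelihood is wanted, prespecify it for all models and rank by penalised LR. Switching estimator only after an empty cell is seen would make the method depend on the outcome data, in a plan written to prevent selective reporting. Firth with Wald tests repairs the problem only in part (8/8 with N = 200 and 20 events: 11.3 minus-df units, against 37.4 for penalised LR).

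The cost is SAP wording, slightly more computing (each model is refitted without each factor in each imputed dataset) and a pooled LR test. No new data are needed.

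### The combined model's variables appear to be chosen on the outcome in the same patients, so any ordinary p-values and 95% confidence intervals reported for it would not be valid

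*SAP*

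**What the plan says.** The section Statistical Principles describes three logistic models. The first uses patient- and injury-related variables and the second uses treatment-related variables. The third is "a combined model which include 3–4 most important variables from the first analysis combined with the 3–4 most important from the second model". The same section says "Variable importance is also assessed using Wald chi-squared test minus degrees of freedom" and names no other importance measure. It adds "When appropriate, 95% confidence intervals will be calculated, and associated p-values calculated", without naming the models this applies to, and sets multiplicity aside: "Multiplicity is not considered since we are not focused in single regression coefficients nor we have specific multiple testing".

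Study Methods says that both articles rest on one patient dataset, so ranking and refitting share the same patients and outcomes. The performance outputs named are R² and calibration plots. The SAP names no bootstrap, cross-validation, shrinkage or sample split.

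Objectives and Hypotheses describes the combined model differently, as "combining the treatment-related risk factors and the three most important patient- and injury-related predictive factors from the first study". There, only the patient and injury factors are selected, and exactly three of them.

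**The concern.** The reason given for setting multiplicity aside suits the first two models, whose candidates come from the literature and are fitted together. It does not suit the third. Membership of that model is decided by ranking individual variables on a statistic computed from the outcome, and the model is then fitted to the same data. A variable that was kept because its statistic was large no longer has a p-value that is uniform under the null, or an interval with nominal coverage.

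Two things are at stake. Noise variables that enter the combined model would reach p<0.05 far more often than 5% of the time. Coefficients of real predictors that are selected would be exaggerated on average, which makes predicted risks too extreme: too high for high-risk patients and too low for low-risk patients. The SAP's introduction intends the prediction model for advising patients and planning follow-up.

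**Working it through.** The SAP states no sample size, event count or error rate, so there is no figure of its own to reproduce.

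**Inputs from the SAP**
- Table 2, patient factors: "Age at the date of injury - Sex - Body mass index - Diabetes - Smoking", which is 5.
- Table 2, injury factors: AO/OTA class, periprosthetic fracture, open or closed fracture, and "Trauma energy - Fracture zone length - Segmental comminution (AO/OTA A3, C2, C3) - Medial comminution of the fracture", which is 7 in all. The first model therefore has 12 candidates.
- Table 2, treatment factors: 8 candidates for the second model.
- Selected: 3 or 4 from each (Statistical Principles), or 3 of 12 plus all 8 treatment factors (Objectives).
- Two-sided 5% level, implied by the 95% intervals.

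**Assumptions**
The 12 and 8 are counts before redundancy analysis and data reduction. Each candidate is treated as having one degree of freedom, although AO/OTA class and proximal fixation mode may use more.

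**Null case, by formula**
With m independent null candidates, the number X with p<0.05 is Binomial(m, 0.05). If the k largest statistics are kept, the false-positive rate per kept variable is E[min(X,k)]/k = (1/k) × Σ P(X ≥ j), for j = 1 to k.

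| m | P(X≥1) | P(X≥2) | P(X≥3) | P(X≥4) | k = 3 | k = 4 |
|---|---|---|---|---|---|---|
| 12 | 0.4596 | 0.1184 | 0.0196 | 0.0022 | 0.5976/3 = 19.9% | 0.5998/4 = 15.0% |
| 8 | 0.3366 | 0.0572 | 0.0058 | 0.0004 | 0.3996/3 = 13.3% | 0.4000/4 = 10.0% |

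- Averaged over the combined model: (19.9 + 13.3)/2 = 16.6% for 3+3, and (15.0 + 10.0)/2 = 12.5% for 4+4.
- On the Objectives reading: about 20% for each of the three selected variables and 5% for the eight unselected ones, which averages (3 × 19.9 + 8 × 5)/11 = 9.1%.

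**Null case, by simulation**
The procedure was run as written: fit both models, rank by Wald chi-squared, refit the selected set, and use ordinary Wald intervals. N was 200 or 300, nonunion was 6–22% and correlation was 0 or 0.3, all assumed. The nonunion range follows the rates cited in the SAP's introduction.
- False-positive rate per selected variable: 17.4–19.5% for 3+3 and 13.4–14.8% for 4+4.
- Coverage of 95% intervals: about 82% for 3+3 and 86% for 4+4.
- When the same number of variables is chosen without the outcome: 4.7–5.5% false positives and coverage of about 95%. Selection is therefore the cause.

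**With real predictors**
Three true predictors per block were assumed, with an odds ratio of 1.6 per SD, N 200–300 and nonunion 10–20%, keeping 3+3 or 4+4.
- Selected noise variables with p<0.05: about 21–43%.
- Pooled coverage: about 87–92%.
- Coverage for selected true predictors: about 95–97%.
- Median overstatement of selected true log odds ratios: about 8–35%. In a prespecified model the overstatement is still 3–7%, so that part is small-sample bias and not selection.

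**The case against.** Several points on the other side stand.
- **The ranking rule is inferred.** No sentence says that Wald chi-squared minus degrees of freedom decides which variables are kept. It is the only importance measure named, and any other ranking on the outcome in the same patients would raise the same problem.
- **Reporting is not promised.** Intervals and p-values come only where appropriate, with no model named and no significance rule. A reader might infer that noise variables will be published as significant predictors. The SAP does not support that; it only leaves the door open. The open discretion is a reason to settle the text.
- **The Objectives differ.** On that definition the eight treatment factors are not selected, and the model is called secondary.
- **The null figures are a reference case.** The candidates come from earlier literature, and redundancy analysis may shorten the list. With nine candidates and four kept, the null rate is 11%.
- **Multiple testing and selection are different matters.** Deleting the multiplicity sentence would not by itself correct anything.

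A reader might also infer that every interval in the combined model is too narrow. The simulations do not show that. Selected true predictors keep near-nominal coverage, and the shortfall falls on selected noise variables, whose estimates are pushed away from zero.

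The reply that the aim is purely predictive meets only part of the point. Exaggerated coefficients carry into predicted risks, and no planned step corrects for this.

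**Conclusion.** The point holds in conditional form. If ordinary p-values and 95% intervals are given for the combined model, they are not valid for the variables selected on the outcome. Under the null the false-positive rate is two to four times nominal (10–20% against 5%), and it changed little over the sample sizes and event rates tried. With real predictors, the size depends on assumptions that the SAP cannot confirm: sample size, event rate, effect size and independence of predictors. The exaggeration of real coefficients is largest with few events and overlaps with the general optimism of a model selected and assessed on one dataset. On the Objectives reading the invalidity is confined to three variables. The full first and second models are not affected by this selection step.

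**What to change.** 1. Reconcile Objectives with Statistical Principles on how the combined model is formed: which blocks are selected from, and whether three or four variables are kept.
2. State the ranking rule in one sentence.
3. Limit the multiplicity rationale to the full prespecified first and second models, and take coefficient intervals and p-values only from those.
4. For the combined model, report no p-values and no ordinary confidence intervals. Repeat imputation, ranking, selection and refitting in each bootstrap resample, and report inclusion frequencies, rank intervals, and optimism-corrected performance and calibration. If bootstrap coefficient intervals are shown, say that they display instability and need not have exact 95% coverage.

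Naming the combined model's variables from the literature before any model is fitted would also remove the problem.

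The cost is SAP wording and a loop around code already planned. No new data are needed. The downside is a little more computing and less favourable reported precision.
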